Preliminary study of functional connectivity changes in substance dependence: As part of [name] (faculty sponsor) research on long term abstinent substance dependent individuals (SDI). I investigated RS-fMRI network connectivity between substance dependent individuals (SDI) and healthy controls (Figure 2). These SDI are unique in that they had prolonged remission of >1 year on average. Group independent component analysis was performed on 50 SDI and 50 healthy controls, and the number, direction, and strength of connections between components identified as standard resting-state networks were analyzed using Granger causality. Compared to controls, SDI showed greater Granger causal connectivity from right executive control network (RECN) to dorsal default mode network (dDMN) and from dDMN to basal ganglia network (BGN). Interestingly, the insula was incorporated in the BGN networks. We concluded that directed effective connectivity from the RECN to dDMN and dDMN to BGN in long term abstinent SDI may reflect higher topdown control from structures involved in executive function and behavioral monitoring over those involved in self-referential thought and reward. I presented these data at the International Neuropsychological Society 2015 Meeting. These results demonstrate our ability to conduct RSfMRI network connectivity analyses which we plan to implement in secondary analyses, in addition to the primary seed-based methods shown above (Figure 2).

**Figure 2.** Left panels, directed Granger causal matrices for SDI (n=50) and controls (n=50). Colorbar corresponds to logarithm of F values. Right panels, network density topological graphs of SDI and controls. Thickness of each line corresponds to the Granger causal strength and color corresponds to the efferent network.

Preliminary study of neuronal response to appetitive food cues compared to neutral cues (Tregellas et al. 2013): [name] (co-sponsor) has extensive experience measuring the neuronal response to visual stimuli of foods of high hedonic value as compared to non-food stimuli,42 demonstrating robust cue-induced activation in the insulae (Figure 3). I plan to use an identical visual cue paradigm, but will replace the food-cue images with images from the international smoking image series.43

stimuli of foods of high hedonic value as compared to non-food stimuli, demonstrating robust cue-induced activation in the insulae.

# IV. Research Methods

**A. Outcome Measure(s):** Outcome measures will include (1) cigarette craving measures, (2) resting-state fMRI connectivity measures, and (3) tasked-based fMRI insular activity measures.

A.1 Neuropsychological Testing: Our primary cognitive outcome will be the change after treatment compared to before treatment in the Questionnaire of Smoking Urges – Brief Version (QSU-brief), a measures craving. An additional important question is whether craving, smoking history, smoking characteristics, or personality traits are associated with specific changes in connectivity after treatment. Thus, we will perform the following assessments prior to treatment: (1) smoking history questionnaire, (2) Fagerstrom nicotine dependence scale (FNDS), (3) Wisconsin inventory of smoking dependence motives (WISDM-68), (4) behavioral inhibitory scale and behavioral activation scale (BIS/BAS), (5) Barratt impulsiveness scale (BIS-11). The QSU-brief will be administered before and after treatment. A visual analog scale will be used to quickly assess subjects' craving during the craving visual-cue task:

The craving data before and after treatment will be used to investigate Aim #1.

A.2. Magnetic Resonance Imaging. All MRI scans will be acquired using a 3.0 T Seimens Skyra MR system using a 20-channel head-neck coil. High-resolution 3D T1-weighted scans will be acquired before treatment for image registration and normalization. T2\* weighted echo-planar imaging blood oxygen level dependent fMRI will be acquired with 3.4 x 3.4 x 3.4 mm voxels, TR 2100 ms, TE 30 ms, and flip angle 70°. Two fMRI sequences will be acquired before and after treatment: (1) a 10 minute RS-fMRI, in which subjects will be asked to lie quietly in the scanner and not think of anything in particular; and, (2) a 15 minute task-based fMRI exam during a cigarette craving cue task. fMRI data will be processed and analyzed as described in the methods section (see C.4 through C.8). Briefly, outcome measures will include insular functional connectivity (see **Aim #3**) changes at the whole brain level after treatment compared to before treatment.

# **B.** Description of Population to be Enrolled:

**Sample Population Recruitment:** Current smokers reporting motivation to quit will be recruited from the University of Colorado Behavioral Health & Wellness Program (BHWP). BHWP in conjunction with the University of Colorado Hospital provides consultation and treatment of tobacco dependence through their Tobacco Free Program. Subjects for this study will be recruited from the pool of patients considering enrolling in treatment through BHWP at the University of Colorado Hospital. [name] is the director of BHWP; he or his clinical colleagues will ask each patient being seen by the Tobacco Cessation Team if they are interested in participating in a research study, and if so, they will be provided a flyer that includes basic information as well as [name] contact information. The flyer will instruct interested prospective subjects to call or e-mail [name] to set up an appointment. This appointment will allow [name] to discuss the study with the participant in a private office maintained by the Department of Radiology, answer any questions the participant may have, and obtain informed consent. Public advertising for this study will also be performed using flyers with pull-off tabs (e.g., downtown public areas, convenience stores with permission of the owner) and newspaper/internet ads (e.g., Craig's List, Denver Post). All

advertising will comply with the COMIRB Advertising Components Submission Form without any deviation.

Inclusion criteria:

- 1) Age 18-55
- English proficient
- 3) Ability to provide informed consent
- 4) Self-reported current average daily cigarette consumption >10/day for at least 1 year
- 5) Self-reported motivation to quit smoking

Exclusion criteria:

- 1) MRI/TMS exclusions, including
  - a. Claustrophobia
    - b. Intracranial or spinal hardware
    - c. Pacemakers
    - d. MR-incompatible devices (Examples: pacemaker, deep brain stimulator, vagal nerve stimulator, cochlear implant, insulin pump, implanted medication pump, bone stimulator, implanted defibrillator)
    - e. History of metal objects or fragments in the eye or skull, including shrapnel or metal plates
    - f. History of stroke or other brain lesion
    - g. History of attempted suicide or suicidal ideation
    - h. Personal history of headaches, seizures, epilepsy, or status epilepticus
  - i. Family history of epilepsy
  - j. Medications known to lower seizure threshold (e.g., tricyclic antidepressants, antipsychotics, psychostimulants)
  - k. Increased intracranial pressure, hydrocephalus, or pseudotumor cerebri
  - I. Unstable coronary artery disease
  - m. Current pregnancy or positive urine pregnancy test
- 2) Neurological illness
- 3) Prior neurosurgery
- 4) Schizophrenia
- 5) Bipolar disorder
- 6) Current (within the last two months) major depressive disorder
- 7) Substance dependence (except cannabis) or positive urinalysis for opiates, stimulants, or sedative on the day of testing
- 8) Alcohol dependence or positive breath test for alcohol on the day of testing
- 9) Use of tobacco products other than cigarettes.

Subjects will be randomized to one of two treatment groups: 1) sham TMS, or 2) inhibitory (1 Hz) TMS targeting the insula.

#### C. Study Design and Research Methods

#### **Experimental Method for all Aims:**

C.1 Enrollment. Prior to informed consent, the inclusion and exclusion criteria will be reviewed with each subject. Once eligibility has been determined, each subject will be provided with verbal and written informed consent. All questions will be answered.

Each subject will participate in a single session, during which inclusion and exclusion criteria will be reviewed, the subject will provide informed consent, women will be have urine pregnancy screens, urine and breath drug and alcohol tests will be administered, standardized psychological assessments will be performed, and then resting and task-based fMRI scans before and after rTMS. The following is the projected timeline for a given subject's study appointment:

Stud	y Appointment Component	Duration (min)		
1.	Review of inclusion and exclusion criteria	10		
2.	Informed Consent	15		
3.	Urine and breath tests	5		
4.	Pre-treatment neurological examination	10		
5. Initial standardized surveys				
6. Pre-treatment MRI examination 49				
	High- definition structural T1W sequence	6		
	Resting-state fMRI sequence	10		
	Craving-cue task fMRI sequence/task	15		
	Magnetic Resonance Spectroscopy (MRS)	18		
7.	Walk to TMS Laboratory	5		
8.	rTMS Treatment	31		
9.	Walk to Brain Imaging Center	5		
10.	Post-treatment MRI examination	43		
	Resting-state fMRI sequence	10		
	Craving-cue task fMRI sequence/task	15		
	Magnetic Resonance Spectroscopy (MRS)	18		
11. Post-treatment QSU-Brief 2				
12.	Post-treatment neurological examination	10		
	Total:	205		

Subjects will be asked to remain abstinent from smoking for 3 hours prior to the study. Subjects will provide urine samples to screen for recent drug use and quantify urine cotinine levels. To ensure abstinence they must fill a questionnaire, test negative for alcohol by a breath screening test, and have a breath CO<10pp. Clinical assessment including a brief medical and psychiatric interview will be performed by [name] to determine eligibility. Subjects will undergo a brief (10 minute) neurological examination. Subjects will be educated on TMS and MR safety and will demonstrate their understanding.

C.2 Demographic. Psychological, Smoking, and Craving Assessments: Subjects will complete a basic demographic survey to document the date of birth, sex, ethnicity, education, handedness, and use of glasses. Age and sex must be determined because gray matter characteristics and brain function vary by age. Education and handedness must be documented because brain function is affected by these variables. The use of glasses must be documented because if subjects are unable to see the images during the craving cue task, it can introduce a bias in the data.

Medical history, current medications, and surgical/procedural history will be documented. [name] will review this information to ensure that the subject meets no exclusion criteria, and to ensure that the subject is taking no medications that lower the seizure threshold.

Subjects will complete a brief smoking history questionnaire. This will characterize the severity and nature of the subject's cigarette dependence, which may affect their responses to craving cues.

Subjects will complete the Fagerstrom Nicotine Dependence Scale (FNDS). This is a valid and reliable standardized survey to quantify the degree of cigarette dependence.

Subjects will complete the Wisconsin Inventory of Smoking Dependence Motives (WISDM-68). This is a valid and reliable 68-item standardized survey designed to characterize the psychological constructs that motive an individual subject's smoking behaviors.

Subjects will complete the Questionnaire on Smoking Urges – Brief (QSU-Brief). This is a valid and reliable standardized survey to quantify a subject's current intensity of craving. This is the only standardized survey that in addition to being administered prior to rTMS treatment will also be administered after rTMS treatment.

Subjects will complete the Behavioral Inhibition Scale and Behavioral Activation Scale (BIS/BAS). The Behavioral Inhibition and Activation Scale is a 20-item self-reported questionnaire

used to measure responsiveness of motivational systems. The first component is the Behavioral Inhibition Scale, which is used to quantify avoidance behaviors and reactions to the anticipation of punishment. The second component is the Behavioral Activation Scale, which is used to quantify positive affective and approach response tendencies to appetitive stimuli.

Lastly, subjects will complete the Barratt Impulsiveness Scale, version 11 (BIS-11). This is a 30-item self-reported questionnaire used to measure impulsivity; subjects rated whether phrases and words describing aspects of impulsivity are self-descriptive.

*C.2 MRI scan acquisition parameters:* Prior to the MRI scan, subjects will be asked to complete the standard *UC Denver Brain Imaging Center MRI Research Subject Screening Form* to ensure they are safe to be scanned. Before and after rTMS, RS-fMRI and task-based fMRI examinations will be performed. This is a required component of any MRI examination. All scans will be performed on a research-dedicated 3.0 T Seimens Skyra MR system using a 20-channel head-neck coil. A VacFix head-confirming vacuum cushion will mitigate effects of head motion. High-resolution 3D T1-weighted scans will be acquired before treatment for image registration and normalization. Linear and second order shimming will be performed to reduce static field inhomogeneities at the skull base prior to fMRI scans. T2\* weighted echo-planar imaging blood oxygen level dependent fMRI will be acquired before and after treatment: (1) a 10 minute RS-fMRI, in which subjects will be asked to lay quietly in the scanner and not think of anything in particular; and, (2) a 15 minute task-based fMRI exam during a cigarette craving cue task.

C.3 1H-Magnetic Resonance Spectroscopy (MRS): Before and after rTMS, 1H-MRS examinations will be performed to quantify GABA, Glutamate, and Glutamine levels in the insula. 1H-MRS sequences will be used, as previously reported and used by colleagues in the Department of Radiology. This MR sequence will be used for exploratory analysis.

C.3 rTMS Treatment: Subjects in the insular rTMS treatment arm will undergo a single 25 minute train of 1Hz rTMS targeting the right insula16,17,54 anterior (MNI coordinates: [32, 18, 4]) at 90% motor threshold using the commercially available MagStim coil Brainsight Rapid2 and frameless stereotactic TMS localization system. Subjects in the sham rTMS treatment arm will have a sham coil placed in the same position. The sham coil

creates sound, vibrations, and electrical stimulation similar to the active coil. Subjects will undergo a brief (10 minute) neurological examination by [name] before and after rTMS treatment, which will include examination of the motor, sensory, language, abstract-thinking, memory, and spatial reasoning systems.

The specific parameters of the rTMS proposed in this study are as follows:

Parameter	Value
Manufacturer	MagnaStim
Model Name	Rapid2
510(k) or Master File Number	
Amplitude (% of motor threshold)	90%
Frequency (pulses per second) [a]	1 Hz

Train duration [b]	1500 sec (25 min)
Number of trains per session [c]	1
Number of sessions in study [d]	1
Cumulative exposure (total # of pulses = $a \times b \times c \times d$ )	1500 pulses
Intertrain interval (time between trains)	N/A

The following table is the maximum safe duration (in seconds) of a single train of rTMS, reproduced without permission from Rossi et al. Here, safety was defined as absence of seizure, spread of excitation or afterdischarge of EMG activity. Numbers preceded by > are the longest duration tested. This table was presented by consensus. The parameters proposed in our study are highlighted in yellow and well within safe limits.

Erog (Hz)	Intensity (% of motor threshold)					
Fied (EZ)	90%	100%	110%	120%	130%	
1	>1800	>1800	>1800	>360	>50	
5	>10	>10	>10	>10	>10	
10	>5	>5	>5	4.2	2.9	
20	2.05	2.05	1.6	1.0	0.55	
25	1.28	1.28	0.84	0.4	0.24	

C.4 Comparison of craving responses to treatment: QSU and visual-analogue craving measures will be compared using a multivariate analysis of covariance (see C.4.1.1). These comparisons will provide results for **Aim #1**.

C.5 Image preprocessing: Raw BOLD data will be pre-processed using SPM8 (website: http://www.fil.ion.ucl.ac.uk). After discarding the first four volumes for saturation effects, motion correction will be applied with a 3D rigid body transformation. Subjects with head movement >2mm will be excluded. fMRI images will be spatially normalized to Montreal Neurological Institute (MNI) space by registering each subject's fMRI images to their high resolution T1W scan, which will be registered to MNI space using the DARTEL method. Registered fMRI images will be spatially smoothed using a 4mm FWHM isotropic Gaussian kernel. Band-pass filtering (0.01Hz–0.08Hz) will be applied to reduce effects of low frequency drift and high-frequency physiologic noise. fMRI data will be corrected for movement parameters (3 rotational and 3 translational variables) as well as global, CSF, and white matter signal fluctuations.

C.6 Seed Based Insular Functional Connectivity: Using customized MATLAB scripts, whole brain voxel-wise connectivity maps will be calculated according to Margulies et al. from the 10 minute RS-fMRI exams using a seed-based approach with a 5mm radius sphere centered at the right anterior insular rTMS target. To compare insular connectivity, first we will apply a fixed-effects analysis to each subject's resultant whole-brain insular connectivity maps to investigate individual brain connectivity differences associated with treatment. Treatment and group comparisons will be performed using ANCOVA. These comparisons will provide results for **Aim #2**.

C.7 Craving cue task-based insular activity: After resting state fMRI examinations, all subjects will perform smoking cue/neutral cue craving tasks during a 15 minute fMRI using the aforementioned imaging parameters. We have previous experience using this task to elicit food craving. We will use an identical visual cue paradigm, but will replace the food-cue images with the international smoking image series. Each run will consist of pseudorandom presentations of different smoking-related and food-related images. Between images, participants will be asked to fixate on a cross image for variable duration of time to introduce jitter into the design and improve fit of the generalized linear model (GLM).

Task-based fMRI exams will be preprocessed as above. Data will be modeled in SPM8 using a GLM with customized square waveforms representing the condition (i.e., cigarette versus neutral stimulus) and duration of stimulus convolved with a canonical hemodynamic response function.

Contrast maps of smoking>neutral cues will be analyzed using second-level random-effects to compare these contrasts within and between treatment groups using ANCOVA. Two separate task-based analyses will be performed: (1) insular ROI analyses by extracting insular activity from the fMRI with a 5mm radius sphere centered at the insular TMS target, and (2) whole brain analysis. Both analyses will control for multiple comparisons using cluster-based correction for family-wise error p<0.05. These comparisons will provide results for **Aim #3**.

C.8 Resting state network analysis (secondary): One inherent limitation of the seed-based connectivity approach is that the resultant connectivity maps are highly dependent upon ROI selection. To circumvent the potential interference caused by seed selection, secondary investigation of the functional connectome will be performed using group independent component analysis to make inferences using the GIFT toolbox (http://icatb.sourceforge.net) and using the same method and analysis pipeline as our preliminary data. Resultant resting state network connectivity maps will be compared by group to investigate differences in strength and direction of connectivity between salience, default mode, and executive control networks.

C.9 Brain-behavior relationships (secondary): Secondary analysis of brain-behavior relationships will be conducted using a GLM in SPM8 by regressing insular connectivity and activity (see C.3.6) against craving and dependence measures. This will characterize the relationship between behavior (**Aim #1**) and brain function (insular connectivity [**Aim #2**] and activity [**Aim #3**]).

C.10 Relative concentrations of GABA, glutamate, and glutamine after rTMS (exploratory): Exploratory analysis of the changes in GABA, glutamate, and glutamine concentrations induced by rTMS will be performed using spectroscopic peak detection methods and ANCOVA.

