# AIM 1. Determine if insular rTMS reduces cigarette craving.

H1 Compared to sham, insular rTMS will reduce craving in response to cigarette cues.

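### Does a QSU-brief baseline taken before any cue task, set against a final reading taken after two, undermine the primary craving comparison?

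*Combined protocol and SAP*

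**What the plan says.** Section A.1 (Neuropsychological Testing) names the outcome: "Our primary cognitive outcome will be the change after treatment compared to before treatment in the Questionnaire of Smoking Urges", in its brief version. Section C.2 lists the QSU-brief among the pre-treatment surveys and says it is the only one repeated after rTMS.

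The order of events comes from the C.1 table, introduced as "The following is the projected timeline" for one appointment. The baseline form belongs to "5. Initial standardized surveys". The pre-treatment MRI, with its cue task, follows as step 6. The next row is "Walk to TMS Laboratory", so no QSU-brief stands between that scan and rTMS. The post-treatment MRI repeats the cue task, and then comes "11. Post-treatment QSU-Brief 2", where the final 2 is the duration in minutes. On smoking, C.1 states: "Subjects will be asked to remain abstinent from smoking for 3 hours prior to the study".

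H1 reads: "Compared to sham, insular rTMS will reduce craving in response to cigarette cues". Section F.1.1 models craving before and after treatment jointly, with treatment assignment and FTND as predictors. It tests the treatment-by-time interaction and the two main effects. Section A.1 also provides a second craving measure: "A visual analog scale will be used to quickly assess" craving during the cue task. Section C.4 puts it into the Aim 1 analysis together with the QSU.

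**The concern.** H1 is about craving provoked by cigarette cues, yet the primary change score starts from a reading taken before any cue was shown and ends with one taken after two cue tasks. Cue exposure and longer abstinence may each raise craving whatever the coil does. A change from uncued to cued craving thus seems to measure something other than the treatment effect.

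Three things would be at stake if this mattered: a biased comparison with sham, a primary outcome that misses the construct in H1, or a noisier change score in a trial of 20 per arm. The remedy looks cheap: one more 2-minute form on leaving the scanner after the pre-treatment MRI.

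**Working it through.** **1. The plan's own figures.** Section F.1.2 cites effect sizes of 3.0 (active) and 1.9 (sham), a difference of 1.1. A two-sample t-test at two-sided 0.05 and 80% power needs 14.002 per arm, rounded up to the stated 15. With 10% loss, 20 × 0.9 = 18 per arm remain. The detectable effect is then 0.961, against the stated 0.962. Both reproduce, and F.1.2 does not say whether they assume a cued or an uncued baseline.

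**2. The schedule.** The rows of the C.1 table other than step 5 give 10+15+5+10+49+5+31+5+43+2+10 = 185 minutes. The stated total is 205, so the surveys take 205 − 185 = 20 minutes, from minute 40 to minute 60. The final QSU-brief starts at 60+49+5+31+5+43 = minute 193. That is 193 − 60 = 133 minutes after the surveys end and 193 − 40 = 153 after they begin. If smoking stopped exactly 3 hours before the visit, abstinence is 180+40 = 220 to 180+60 = 240 minutes at baseline and 180+193 = 373 at the end. The asymmetry is real.

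**3. Bias.** Let B be any craving reading before rTMS and P the final reading. The treatment-by-time contrast estimates

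(E[P | active] − E[P | sham]) − (E[B | active] − E[B | sham]).

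Allocation is random and B precedes rTMS, so the second bracket is zero in expectation, cued or not. What remains is the arm difference in the final reading, which is taken after a cue task. Adjusting for FTND, also measured before treatment, does not alter this. Nor must the cue effect be a constant shift: if rTMS dampens the response to cues, that shows in P.

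A simulation with 20,000 replicates and 18 per arm illustrates this. The pre-post correlation was assumed to be 0.7 in the first row and 0.5 in the others.

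| Shift common to both arms (SD) | Estimate, true effect 0 | Estimate, true effect −0.962 |
|---|---|---|
| 0 | −0.003 | −0.962 |
| 0.5 | 0.000 | −0.961 |
| 1.0 | −0.005 | −0.957 |

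**4. Construct.** By step 3 the expected contrast is the same number with either baseline. A cued baseline therefore cannot bring the test closer to H1.

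**5. Precision.** Take a simple model with stable craving C, cue reactivity R1 and R2 (variance sR², correlation r) and error variance se².

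- Uncued baseline: variance of change = 2se² + sR².
- Cued baseline: variance of change = 2se² + 2sR²(1 − r).

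They are equal when 1 = 2(1 − r), that is r = 0.5. With sR² = se² = 1, uncued against cued gives 3.00 and 3.50 at r = 0.25, 3.00 and 3.00 at r = 0.5, and 3.00 and 2.50 at r = 0.75. These values of r are illustrations, since the documents give none. The break-even also depends on the model, which assumes that reactivity is unrelated to stable craving and has equal variance after one and two tasks.

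**6. How far an extra form would match the readings.** It would start at 60+49 = minute 109, and the final form at 109+2+5+31+5+43 = minute 195. Start to start, the gap would be 86 minutes. The present gap, counted the same way for a 2-minute form within the surveys, is 193 − 58 = 135 to 193 − 40 = 153. Cue tasks before the two readings would be 1 and 2, and abstinence 180+109 = 289 and 180+195 = 375 minutes. The readings would be closer but still unequal.

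**The case for a change.** The strongest counter-argument concerns the main effect of time, which F.1.1 also tests. Randomization does not protect it. With a common shift of 1.0 SD and a true effect of −0.962, the simulation gave a mean change of +1.00 in the sham arm and +0.04 in the active arm. A reader of the active arm alone would see no benefit where there is one.

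That much stands: the time effect and within-arm changes cannot be read as treatment effects. But no section reads them so. H1 is a comparison with sham, and the interaction tests it. An added form would not cure the time effect either, because cue exposure and abstinence would still differ.

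It can also be said that the form costs 2 minutes, taking the visit from 205 to 207, and might improve precision. It might, but the direction is unknown. The form would also create a second candidate baseline for the primary outcome and require a choice between them.

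Finally, the visual analogue scale does not replace the QSU-brief as the named primary measure. True, but the cue task runs before and after rTMS, so on the natural reading the scale already gives craving under the same task at both times.

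**Conclusion.** The concern does not hold. The readings differ in cue exposure (0 tasks against 2) and are more than two hours apart, but this is the same in both arms and cancels in the treatment-by-time contrast. The expected bias is zero with either baseline, and the construct tested is identical. Any effect on precision could go either way and cannot be sized from the documents. Using the uncued reading as baseline is a legitimate design choice.

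This rests on three assumptions: random allocation with the same schedule in both arms, as the protocol describes; arms that remain comparable among those analysed; and an uncued baseline. The last is inferred from the order of the C.1 table, since A.1 and C.2 say only that the form precedes treatment. If it were in fact completed after the first cue task, the asymmetry would shrink and the conclusion would be the same.

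### Aim 3 cue-task scans go through the resting-state pipeline (0.01–0.08 Hz band-pass and global-signal correction), which costs sensitivity and can shrink the smoking-minus-neutral contrast

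*Combined protocol and SAP*

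**What the plan says.** C.5 sets out a single preprocessing sequence. On temporal filtering it says "Band-pass filtering (0.01Hz–0.08Hz) will be applied to reduce effects of low frequency drift and high-frequency physiologic noise". It then corrects the data for six movement parameters "as well as global, CSF, and white matter signal fluctuations".

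C.7 describes the cue task. On image order: "Each run will consist of pseudorandom presentations of different smoking-related and food-related images". Between images, participants are "asked to fixate on a cross image for variable duration of time to introduce jitter into the design". The task scans are then dealt with in one line: "Task-based fMRI exams will be preprocessed as above". The first-level model uses square waves for the condition and "duration of stimulus convolved with a canonical hemodynamic response function", fitted in SPM8. The Aim 3 measure follows: "Contrast maps of smoking>neutral cues will be analyzed using second-level random-effects to compare these contrasts within and between treatment groups using ANCOVA". It is taken both in an insular sphere and over the whole brain.

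No section exempts the task scans from the band-pass or the global-signal correction, says that the design matrix gets the same filter, or plans an Aim 3 analysis without global-signal correction. F.3.1 refers back to Aim 2 only for multiplicity and nuisance variables. C.7 calls the comparison images food-related in one sentence and neutral in others. That affects what the contrast means, but not the filter arithmetic below.

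**The concern.** A narrow low-frequency band is a common choice for resting-state connectivity, where no stimulus has a known time course. A jittered cue task does have one, and part of the modelled response lies outside 0.01–0.08 Hz. If that part is removed from the data but left in the model, the fitted amplitude is too small. Even when both are filtered alike, usable signal is lost.

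The global signal raises a separate, conditional problem. If the brain-wide average responds more to smoking cues than to comparison cues, regressing it out before the GLM subtracts part of the contrast that Aim 3 is meant to estimate.

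What is at stake is the sensitivity of Aim 3. Section G says that finding no difference in craving or fMRI will be read as the insula being less critical than the literature reports. That reading is weaker if the preprocessing has discarded part of the insular response.

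**Working it through.** **Inputs from the documents.** TR 2.1 s and a 15-minute task run (A.2); first four volumes discarded and band 0.01–0.08 Hz (C.5); random order, jitter and canonical HRF (C.7); d above 2.3, more than 5 per arm, analysable N of 32 (F.3.2).

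- Volumes: 900 / 2.1 ≈ 428, less 4 = 424.
- Highest resolvable frequency: 1 / (2 × 2.1) = 0.238 Hz. The band keeps (0.08 − 0.01) / 0.238 ≈ 29% of the frequency range.

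**Assumptions.** The documents give neither cue duration nor gap length. I take cues of 2–6 s, gaps of 1–12 s, a double-gamma HRF and AR(1) noise of 0.2–0.4 without a cardiac or respiratory component. The 128 s high-pass used as comparator is also an assumption; the documents name none.

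**The plan's own figure.** A two-sided two-sample t-test at 0.05 with d = 2.3 has power 0.773 at 4 per arm and 0.888 at 5, so the stated 5 per arm reproduces.

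**Filtering.** Let X be the HRF-convolved design, c the smoking-minus-neutral contrast, B the band-pass and β the true amplitudes.

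- Data filtered, design not: fraction retained = c′(X′X)⁻¹X′BXβ / c′β. This is close to 1 − H − L, where H and L are the shares of the contrast regressor's variance above 0.08 Hz and below 0.01 Hz.
- 128 s high-pass kept on the design: about (1 − H − L) / (1 − L₁₂₈), where L₁₂₈ is the share below 1/128 Hz.
- Data and design band-passed alike: retained = 1.

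| Cue, gap (s) | H | L | L₁₂₈ | Retained, design unfiltered (simulated) | Retained, 128 s on design (by formula) |
|---|---|---|---|---|---|
| 2, 1–5 | 0.107 | 0.109 | 0.080 | 0.783 | 0.784 / 0.920 = 0.85 |
| 3, 2–6 | 0.091 | 0.112 | 0.084 | 0.796 | 0.797 / 0.916 = 0.87 |
| 4, 2–6 | 0.073 | 0.121 | 0.090 | 0.807 | 0.806 / 0.910 = 0.89 |
| 4, 4–12 | 0.074 | 0.123 | 0.091 | 0.806 | 0.803 / 0.909 = 0.88 |
| 6, 4–10 | 0.039 | 0.133 | 0.100 | 0.829 | 0.828 / 0.900 = 0.92 |

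Shrinkage is therefore about 17–22% with an unfiltered design. It is 7–15% with the 128 s filter on the design (direct simulation gives 0.85–0.93 retained) and 0% with matched band-passing. About three quarters of the low-frequency share (0.080 / 0.109 = 73%; 0.100 / 0.133 = 75%) would also go under a 128 s high-pass.

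The ratio of mean contrast to its standard deviation, relative to a 128 s high-pass on both data and design, was about 0.90–0.96 in all three cases: a per-subject loss of 4–10%.

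**Global signal.** With y the insular series and g the global series, correction before the GLM gives y − g(g′y)/(g′g). The contrast lost depends on how much of the insular smoking-neutral difference g carries. Two simple simulations give:

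| Hypothetical share carried by g | Contrast lost |
|---|---|
| 0% | none |
| 10% | 9–11% |
| 20% | 21–24% |
| 40% | 42–50% |

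**Power.** With 16 per arm (32 / 2), the effect detectable at 80% power is d = 1.02. If a 10% signal-to-noise loss passed in full to the group effect, power there would fall from 0.80 to 0.71. Between-subject variance would dilute that. At d = 2.3, power stays above 0.99 even with the effect scaled to 0.7.

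**The case against.** The strongest reply is that a scale factor common to both arms and both scans leaves the null hypothesis and the standardised effect unchanged. That stands. The 17–22% shrinkage must not be read as a power loss of that size; the sensitivity cost is the 4–10% loss in signal-to-noise. One could compute a fall in power to 0.61 at d = 1.02 by scaling the effect to 0.8 with noise unchanged, but filtering removes noise too, so that figure is only a worst case.

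A second reply is that the GLM is run in SPM8 and its design may well be high-passed, or filtered to match. The documents do not say, so the honest range for shrinkage is 0–22%, not its upper end alone.

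Third, C.5 gives a reason for the upper cut-off, namely physiologic noise. The simulated noise has no such component, so any benefit from the low-pass is not represented and the net loss could be smaller.

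Fourth, cue responses common to both conditions cancel in the contrast. A reader might infer that global-signal regression necessarily removes part of the Aim 3 effect, or produces a false arm difference. The documents support neither: they give no figure for the share of the smoking-neutral difference in the global signal, and none for any change in the global cue response after rTMS. Leaving global regression out has a cost as well, because true global changes then reach the insular contrast.

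None of these replies supplies the missing task-specific specification.

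**Conclusion.** The concern holds in a limited form. As written, C.7 applies a resting-state band-pass and global-signal correction to a jittered cue task and leaves the filtering of the design unstated. The expected cost from filtering is a per-subject signal-to-noise loss of roughly 4–10%, together with contrast shrinkage between 0% and 22% depending on how the design is filtered. These sizes rest on assumed cue timing and an AR noise model; the direction was the same in every timing tried.

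Filtering alone does not create a difference between arms, and at the plan's own effect size its effect on power is negligible. It would matter for an effect near the detectable limit, and for reading a null insular result.

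The loss from global-signal regression is hypothetical in size and may be zero. It could bias the arm comparison only if rTMS changes the global cue response.

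**What to change.** In C.7, replace the cross-reference to C.5 with a short pipeline for the task data:

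- a high-pass filter only, with its cut-off stated, applied identically to data and design;
- the six motion parameters, and CSF and white-matter signals if wanted, as regressors inside the GLM;
- the primary Aim 3 analysis without global-signal regression, and a sensitivity analysis with it.

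State cue duration and gap range in the same place. Keep the band-pass and global-signal correction for the resting-state scans (Aim 2). Settle this before unblinding, so that preprocessing is not chosen with results in view.

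Matched band-passing of data and design would also remove the shrinkage, but would leave the signal-to-noise loss.

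The cost is a few lines of text, a separate processing setting and one extra sensitivity run, with no new data. The downside is somewhat less suppression of high-frequency physiologic noise in the task scans.
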